9.4.1.1 Time to Improvement of Grade 4 Neutropenia

9.4.1.1.1 Time to Improvement of Grade 4 Neutropenia Present at the Time of Blast Clearance

For subjects whose ANC lab value is $<0.5 \times 10^9/L$ at the time of blast clearance, their time to improvement of Grade 4 neutropenia present at the time of blast clearance is defined as number of days from the blast clearance to the first date of ANC lab value recovered to $\geq 0.5 \times 10^9/L$.

9.4.1.1.2 Time to Improvement of First Grade 4 Neutropenia Onset Post Blast Clearance

For 1) subjects whose ANC lab value is $\geq 0.5 \times 10^9/L$ at the time of blast clearance and for 2) subjects whose ANC lab value is $<0.5 \times 10^9/L$ at the time of blast clearance and is recovered to $\geq 0.5 \times 10^9/L$ post blast clearance, their time to improvement of first Grade 4 neutropenia onset post blast clearance is defined as number of days from the first date when ANC lab value drop to $<0.5 \times 10^9/L$ post blast clearance to the first date when ANC lab recovered to $\geq 0.5 \times 10^9/L$.

9.4.1.2 Time to Improvement of Grade 4 Thrombocytopenia

Analyses will be performed similar to Time to Improvement of Grade 4 Neutropenia.

9.4.1.3 Time to Improvement of Grade 3 Anemia

Analyses will be performed similar to Time to Improvement of Grade 4 Neutropenia.

9.4.2 Duration of Blood Count Improvement

Duration of blood count improvement will be analyzed for subjects who achieved bone marrow blast clearance (CR/CRi/MLFS).

9.4.2.1 Duration of Improvement of Grade 4 Neutropenia Present at the Time of Blast Clearance

For subjects whose ANC lab value is $<0.5 \times 10^9/L$ at the time of blast clearance with a subsequent improvement, the duration of improvement of Grade 4 Neutropenia present at the time of blast clearance is defined as number of days from the first date of ANC lab value recovered to $\geq 0.5 \times 10^9/L$ following blast clearance to the first date when ANC lab value dropped back to $<0.5 \times 10^9/L$.

9.4.2.2 Duration of Improvement of Grade 4 Thrombocytopenia Present at the Time of Blast Clearance

Analyses will be performed similar to Duration of Improvement of Grade 4 Neutropenia.

9.4.2.3 Duration of Improvement of Grade 3 Anemia Present at the Time of Blast Clearance

Analyses will be performed similar to Duration of Improvement of Grade 4 Neutropenia.

9.4.3 Rates of CR or CRi in molecular subtypes

Rates of CR/CRi in molecular subtypes (FLT3-ITD/TKD, IDH1, IDH2, IDH1/2, TP53, NPM1, CEBPA, TET2, ASXL1, DNMT3A, Other) identified per institutional practices will be summarized using summary statistics (N, mean, standard deviation, median, range) for each of the treatment groups.

9.5 Efficacy Subgroup Analysis

Rates of composite complete remission rates (CR + CRi) will be presented along with their exact 95% CI.

The subgroups defined below, not limited to, will be used for these analyses:

1. Gender (Male, Female)
2. Age (12 – < 65 years, 65 – < 75 years, ≥ 75 years)

3. Baseline ECOG (Grade < 2, \geq 2)
4. Type of AML (De Novo, Secondary, Therapy-related AML)
5. Cytogenetic risk (Intermediate, Poor, Favorable)
6. CYP3A inhibitors use leading to venetoclax dose reduction (Yes, No)
7. Antecedent hematologic history of MDS or MPN (Yes, No)

10.0 Safety Analysis

10.1 General Considerations

All analyses in this session will be presented for: venetoclax in combination with azacitidine, venetoclax in combination with decitabine, and all treated subjects combined.

10.2 Analysis of Adverse Events

10.2.1 Treatment-Emergent Adverse Events

Adverse events (AE) with onset or worsening on or after the first dose of study drug and no more than 30 days after the last dose of study drug are treatment emergent. All summaries of adverse events will include treatment-emergent events (TEAE) only unless specified otherwise.

Adverse event data will be coded using the Medical Dictionary for Regulatory Activities (MedDRA). The version of the MedDRA dictionary that is current at the time of summarization will be applied to the codes prior to summarization. AE rates will then be summarized by system organ class (SOC) and preferred term (PT).

Within each summary the following AE rates will be presented:

- Overall rates: subjects who had at least one AE,
- SOC rates: subjects who had a least one event falling in a given system organ class,

- PT rates: subjects who had at least one event with the given preferred term.

For summaries of AE by National Cancer Institute Common Terminology Criteria for Adverse Events (NCI CTCAE v4.03) grade, at each level of summarization (overall, SOC, and PT) each subject is counted only once at the maximum grade level.

Summaries of SAE are described in Section [10.2.3](#).

The number and percentage of subjects experiencing at least one event for each of the following categories will also be summarized:

- Any TEAE
- TEAE with reasonable possibility of relationship to venetoclax per the investigator.
- TEAE with NCI grade 3 or higher
- TEAE with NCI grade 3 or 4
- TEAE leading to discontinuation of venetoclax
- TEAE leading to venetoclax dose interruption
- TEAE leading to venetoclax dose reduction
- TEAE with reasonable possibility of relationship to the HMA per the investigator
- TEAE leading to discontinuation of the HMA
- TEAE leading to HMA dose interruption
- TEAE leading to HMA dose reduction.

Overview tables with overall rates of each of the above AE types plus treatment-emergent death rates will be prepared for TEAE.

10.2.2 SAEs (Including Deaths)

Treatment-emergent serious adverse event rates will be summarized by MedDRA system organ class and preferred term as done for adverse events in general. The summaries of SAE data will include tabulations of the following rates:

- All treatment-emergent SAE
- Adverse events resulting in hospitalization
- Adverse events resulting in death.

Treatment Emergent Deaths

Rates of deaths that occur within 30 days of start of treatment and within 30 days following the last dose of study drug will also be summarized.

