## 3.4 Safety Endpoints

---

Safety evaluations include adverse event monitoring, physical examinations, vital sign measurements, clinical laboratory testing (chemistry, hematology, and coagulation), and rate of hospitalizations observed as measures of safety and tolerability for the entire study duration.

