#### Medical Complaints/Adverse Events and Serious Adverse Events

An adverse event is defined as any untoward medical occurrence in a subject or clinical investigation subject administered a pharmaceutical product and which does not necessarily have a causal relationship with this treatment. An adverse event can therefore be any unfavorable and unintended sign (including an abnormal laboratory finding), symptom, or disease temporally associated with the use of a medicinal (investigational) product, whether or not the event is considered causally related to the use of the product.

Such an event can result from use of the drug as stipulated in the protocol or labeling, as well as from "special situations," which must be reported whether associated with an adverse event or not.

The investigators will monitor each subject for clinical and laboratory evidence of adverse events on a routine basis throughout the study. All adverse events will be followed to a satisfactory conclusion.

An elective surgery/procedure scheduled to occur during a study will not be considered an adverse event if the surgery/procedure is being performed for a pre-existing condition and/or the surgery/procedure has been pre planned prior to study entry. However, if the pre-existing condition deteriorates unexpectedly during the study (e.g., surgery performed earlier than planned), then the deterioration of the condition for which the elective surgery/procedure is being done will be considered an adverse event.

If an adverse event, whether associated with study drug or not, meets any of the following criteria, it is to be reported to AbbVie clinical pharmacovigilance or CRO (as appropriate) as a serious adverse event within 24 hours of the site being made aware of the serious adverse event (refer to Section 4.3 of the Operations Manual for reporting details and contact information):

Death of Subject	An event that results in the death of a subject.
Life-Threatening	An event that, in the opinion of the investigator, would have resulted in immediate fatality if medical intervention had not been taken. This does not include an event that would have been fatal if it had occurred in a more severe form.
Hospitalization or Prolongation of Hospitalization	An event that results in an admission to the hospital for any length of time or prolongs the subject's hospital stay. This does not include an emergency room visit or admission to an outpatient facility.

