## APPENDIX F. RECOMMENDATIONS FOR INITIAL MANAGEMENT OF ELECTROLYTE ABNORMALITIES AND PREVENTION OF TUMOR LYSIS SYNDROME

Abnormality	Management Recommendations
Hyperkalemia (Including Rapidly Rising Potassium)	
Potassium $\geq$ 0.5 mmol/L increase from prior value (even if potassium within normal limits [WNL])	
 
• Recheck potassium, phosphorus, uric acid, calcium and creatinine in 1 hour STAT. If further <math>\geq</math> 0.2 mmol/L increase in potassium, but still < upper limit of normal (ULN), manage as per potassium <math>\geq</math> ULN. Otherwise recheck in 1 hour.
 
• Resume per protocol testing if change in potassium is < 0.2 mmol/L, and potassium < ULN, and no other evidence of tumor lysis.
 
• As determined by the investigator, may recheck prior to hospitalization. If stable or decreased, and still WNL, hospitalization is at the decision of the investigator. Potassium, phosphorus, uric acid, calcium and creatinine must be rechecked within 24 hours.
 

Potassium > upper limit of normal	
 
• Perform STAT ECG and commence telemetry.
 
• Nephrology (or other acute dialysis service) notification with consideration of initiating dialysis.
 
• Administer Kayexalate 60 g (or Resonium A 60 g).
 
• Administer furosemide 20 mg IV <math>\times</math> 1.
 
• Administer calcium gluconate 100 to 200 mg/kg IV slowly if there is ECG/telemetry evidence of life-threatening arrhythmias.
 
• Recheck potassium, phosphorus, uric acid, calcium and creatinine in 1 hour STAT.
 
• If potassium < ULN 1 hour later, repeat potassium, phosphorus, uric acid, calcium and creatinine 1, 2 and 4 hours, if no other evidence of tumor lysis.
 

Abnormality	Management Recommendations

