4.3.4 Safety Endpoint

Safety evaluations will include adverse event monitoring, clinical lab testing, vital signs measurements, and rate of hospitalization.

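### The rate of hospitalization is a listed safety evaluation, but the SAP tabulates only admissions tied to an adverse event and shows no ramp-up view

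*SAP*

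**What the plan says.** Protocol 3.4 ends its list of safety evaluations with the "rate of hospitalizations observed as measures of safety and tolerability for the entire study duration". SAP 4.3.4 carries this over: "Safety evaluations will include adverse event monitoring, clinical lab testing, vital signs measurements, and rate of hospitalization". Both documents name hospitalization as an item next to adverse event monitoring, and neither restricts it to admissions that an adverse event caused.

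The analysis side is narrower. Apart from that listing, the SAP mentions hospitalization only in 10.2.2, under the sentence "The summaries of SAE data will include tabulations of the following rates", where one of three bullets is "Adverse events resulting in hospitalization". Section 10.2.2 follows the method of 10.2.1, which counts subjects with at least one event overall, per system organ class and per preferred term, and which states that "All summaries of adverse events will include treatment-emergent events (TEAE) only unless specified otherwise". Protocol 7.4, on safety analyses, does not mention hospitalization.

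The only recording route that the documents describe is the serious adverse event report. Its hospitalization criterion (Protocol 6.1) is "An event that results in an admission to the hospital for any length of time or prolongs the subject's hospital stay", so an event has to come first. The activity schedule in Appendix H has no separate item for admissions.

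**The concern.** Protocol 2.1 explains that in the two earlier combination studies patients had to be in hospital for treatment initiation and ramp-up, and that this trial is meant to find out whether venetoclax can be started safely outside hospital. Whether subjects were admitted, above all during ramp-up, bears directly on that question. A reader of the report will take the rate of hospitalization to mean how many subjects were admitted.

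The planned table answers a different question: how many subjects had a treatment-emergent adverse event that led to admission. The two differ whenever a subject is admitted and no adverse event is reported. The protocol itself foresees a case where this can happen. Appendix F covers a rise in potassium that stays within normal limits and says, after a recheck: "If stable or decreased, and still WNL, hospitalization is at the decision of the investigator". One site may report such an admission as a serious adverse event and another may not, and nothing in the documents settles which. The published rate would then depend partly on reporting habits.

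**Working it through.** **1. The plan's own figures.** The documents give no expected hospitalization rate and no precision for it. The one design figure, 13 points of precision with 60 subjects (SAP 4.4), belongs to the remission rate. It reproduces as 1.96 × √(0.5 × 0.5 / 60) = 12.65 points, or 12.40 points at a rate of 60%, and it has no bearing on this point.

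**2. Which admissions reach a table.**

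| Admission | Where it appears under the plan |
|---|---|
| Caused by a reported adverse event, including TLS (Protocol 6.2) | SAP 10.2.2 table |
| Out-of-range laboratory value judged clinically significant and needing treatment (Operations Manual 3.14: recorded as an adverse event) | SAP 10.2.2 table |
| Discretionary, potassium stable and in range (Appendix F) | SAP 10.2.2 table only if the site reports an adverse event; otherwise nowhere |
| Pre-planned elective procedure for an existing condition (Protocol 6.1: not an adverse event) | Nowhere |
| Second event-driven admission of one subject | Does not change the overall rate; identifiable only in the SAE listing (SAP 10.2.4) |
| Any of these during ramp-up | No separate summary |

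**3. Direction.** Subjects with an event-driven admission are a subset of subjects with any admission. Over the same period and denominator, the event-driven rate therefore cannot exceed the all-cause rate.

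**4. Size per subject.** With 60 treated subjects, each subject whose only admission was not event-driven lowers the reported rate by 1/60 = 1.67 points.

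**5. Range under assumed counts.** Suppose 3 to 6 subjects (5% to 10% of 60) have a non-event admission. If none of them also has an event-driven one, the shortfall is 3/60 = 5 points to 6/60 = 10 points. The event-driven counts below are also assumptions; intervals are exact 95%.

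| Event-driven | Reported rate | All-cause, 3 more subjects | All-cause, 6 more subjects |
|---|---|---|---|
| 12/60 | 20.0% (10.8–32.3) | 25.0% (14.7–37.9) | 30.0% (18.8–43.2) |
| 24/60 | 40.0% (27.6–53.5) | 45.0% (32.1–58.4) | 50.0% (36.8–63.2) |
| 30/60 | 50.0% (36.8–63.2) | 55.0% (41.6–67.9) | 60.0% (46.5–72.4) |

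**6. Effect of overlap.** A subject with both kinds of admission is already counted. Protocol 2.1 reports Grade 3 or higher febrile neutropenia in 44% of subjects in the earlier study of this combination. If, purely as an illustration, 44% of the 3 to 6 subjects also had an event-driven admission, the shortfall would be 3 × 0.56 / 60 = 2.8 points to 6 × 0.56 / 60 = 5.6 points. So 5 to 10 points is the ceiling for 3 to 6 subjects.

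**The case against.** The strongest reply is that hospitalization is one of several safety evaluations. It is not a primary, secondary or exploratory endpoint, and the secondary safety objective concerns adverse events. Listed among measures of safety and tolerability, an event-driven rate is a reasonable reading, since an admission for convenience measures neither. That stands as far as importance goes. It does not remove the mismatch, because both documents list hospitalization as an item separate from adverse event monitoring.

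A reader might infer that every precautionary admission is lost. The documents do not support that. The adverse event definition in Protocol 6.1 includes abnormal laboratory findings, an admission of any length makes an event serious, and Appendix F itself files the in-range potassium rise under hyperkalemia in a column of abnormalities. Many such admissions could therefore be reported and counted. What is lost is the admission for which the site reports no event.

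A reader might also infer that repeat admissions vanish, or that no overall rate is planned. Neither is so: SAP 10.2.1 provides an overall subject-level rate, and SAP 10.2.4 lists every serious adverse event record. Counting a subject once is normal for such a rate. What is missing is a summary of how many admissions there were.

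Finally, the eCRF is not among the documents and may already record every admission. If so, the data exist, but the SAP still does not analyse them.

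**Conclusion.** The point holds as a mismatch between a listed evaluation and its only analysis. The planned table can understate the all-cause subject rate and cannot overstate it. The size is 1.67 points per subject whose only admission was not event-driven, with 60 treated subjects assumed. The 5 to 10 points rest on an assumed 3 to 6 such subjects with no overlap, so they are an upper bound under that assumption and not an estimate.

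A reader might go further and say that the trial's conclusion is biased in favour of outpatient initiation. The documents do not support that. No threshold, test or decision rule uses hospitalization, and the stated hypothesis rests on a remission rate of about 60%. What is affected is the accuracy of one reported safety rate, though one that speaks directly to the trial's question. This is a cheap improvement.

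**What to change.** In SAP 10.2.2, define the hospitalization rate as the number and percentage of treated subjects with at least one admission of any length, for any reason, from first dose to 30 days after last dose, with an exact 95% confidence interval. Add the number of admissions per subject. Using any length, and not an overnight stay, keeps the count in line with the seriousness criterion in Protocol 6.1.

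- Split admissions into event-driven, pre-planned elective, and precautionary or other. A subject may fall into more than one class, so the overall rate should be counted directly and not summed.
- Show the Cycle 1 ramp-up period separately, with its window stated. One choice is from first dose to the 24-hour laboratory check after the last escalation.
- Keep the existing adverse event table as a second view.
- Confirm that the eCRF captures the date and reason of every admission, and add a short entry if it does not.

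The cost is one more table, possibly brief data entry from site source records, and possibly a higher stated rate. Sample size, the primary analysis and the rules on when to admit or treat are untouched.

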10.2.3 Selected AEs

Selected AEs will be identified through the search criteria provided in table below and summarized by MedDRA system organ class and preferred term.

Table 1. Selected Adverse Events

Selected Adverse Events	Search Criteria
Tumor Lysis Syndrome* (AE) occurring within 7 days from the first dose study drug	SMQ – "Tumor Lysis Syndrome" (narrow)
Neutropenia*	PT terms – "neutropenia," "neutrophil count decreased," "febrile neutropenia*," "agranulocytosis," "neutropenic infection," and "neutropenic sepsis"
Thrombocytopenia*	PT terms – 'Thrombocytopenia' and 'platelet count decreased'
Anemia*	PT terms – 'Anaemia' and 'Haemoglobin decreased'
Grade ≥ 3 infections	SOC of 'infections and infestations'
Hemorrhages	SMQ - 'Haemorrhages' (narrow)

*Considered as AESI in the protocol.

10.2.4 Listing of SAEs and Deaths

A listing of serious adverse events will be provided. All data from the adverse event records will be compiled into the data listing. A listing of reports of treatment-emergent deaths will also be provided.

10.3 Analysis of Laboratory Data

10.3.1 Variables and Criteria Defining Abnormality

Where applicable, lab test data will be graded according to National Cancer Institute Common Terminology Criteria (NCI CTCAE) version 4.03.

The NCI criteria are ranges of test values that are to be graded from one to four. Lab test results that do not fall into the grade one to four ranges, generally those that are in the normal range for the lab or else are abnormal in the direction opposite the test, will be assigned a grade of zero.

10.3.2 Statistical Methods

For each lab test for which NCI criteria exist, shift tables will be generated that cross tabulate the number of subjects with baseline values of Grade 0, Grade 1, Grade 2, Grade 3, or Grade 4 versus maximum post-baseline of Grade 0, Grade 1, Grade 2, Grade 3, or Grade 4. All treated subjects will be included in the cross tabulation regardless whether baseline or post-baseline measurements are collected.

Separate laboratory shifts tables based on the two criteria below will be generated for each laboratory tests related to CTCAE:

- Shifts from Grade 0 (Normal) at baseline to Grade 1 - 4 Post-baseline (maximum) and worsening from an abnormal baseline value of at least one grade up post-baseline (maximum)
- Shifts from Grade 0 - 2 at baseline to Grade 3 or 4 Post-baseline (maximum) and from Grade 3 at baseline value to Grade 4 post-baseline (maximum).

The maximum NCI grade value is the value with highest NCI grade collected after the first dose of study drug and within 30 days following the last dose of study drug. In cases where multiple values are collected on the same day, the maximum grade value and minimum grade value will be selected as the value for that day for the post-baseline grade value and for the baseline grade value, respectively.

Detailed listings of data for subjects experiencing NCI CTCAE Grade 3 to 4 blood chemistry and hematology values will be provided. All measurements collected, regardless of the number of days after the last dose of study drug, will be included in these listings.

The number and percentage of subjects with liver Enzyme value meeting the criteria for potential drug-induced liver injury ($ALT > 3 \times ULN$ or $AST > 3 \times ULN$ and $TBILI > 2 \times ULN$ within 72 hours [3 days if time stamp is not collected] of each other) will be presented.

The number and percentage of subjects meeting the Howard criteria for TLS will be presented. The Howard Criteria for TLS is defined as two or more of the following treatment-emergent lab changes within a 24-hour period. The evaluation period for TLS is after 1st dose of study drug to 7 days from the 1st dose of study drug.

- uric acid $> 475.8 \text{ mcmol/l}$,
- potassium $> 6 \text{ mmol/l}$,
- inorganic phosphorus $> 1.5 \text{ mmol/l}$
- calcium $< 1.75 \text{ mmol/l}$.

11.0 Summary of Changes Between the Previous Version of SAP and the Current SAP

1. From version 1 to version 2, clarify transfusion independence and conversion rate in Section [4.3.2](#).

2. From version 1 to version 2, clarify molecular marker in Section [7.1](#) and Section [9.3](#).
3. From version 1 to version 2, updated selected AE in Section [10.2.3](#).
4. From version 1 to version 2, updated Section [9.4](#).

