### Prophylaxis and Management of Tumor Lysis Syndrome

There is a potential risk for TLS in subjects with AML, especially in those with elevated leukocyte count, circulating blasts, elevated pretreatment LDH levels, dehydration, or renal dysfunction.

Venetoclax can cause rapid reduction in tumor and thus poses a risk for TLS. Changes in electrolytes consistent with TLS that require prompt management can occur as early as 6 to 8 hours following the first dose of treatment ([Appendix F](#)). Definitions of laboratory TLS and clinical TLS are provided in [Appendix E](#) (Howard grading classification). If a subject experiences blood chemistry changes suggestive of TLS, the dose of venetoclax may be withheld and/or reductions may be required.

Tumor lysis syndrome prophylaxis must be initiated in all subjects before the first dose of study drug or first new escalated dose. For subjects who had dose delay or interruptions TLS prophylactic measures may need to be implemented based on the disease status prior to resuming treatment. Below are the minimum requirements for TLS prophylaxis and management. Additional prophylaxis and monitoring procedures for TLS should be implemented as per institutional/regional standards.

- An oral agent to reduce the uric acid level (e.g., allopurinol) to be initiated at least 72 hours prior to dosing. Treatment may need to be continued for up to 28 days based on the ongoing risk of TLS development. Subjects allergic to or otherwise unable to receive allopurinol must use another uric acid reducer starting at least 72 hours prior to dosing or rasburicase on the day of treatment (prior to venetoclax dosing).
- Adequate hydration per day starting from at least 24 hours prior to first dose or any dose escalation.
- TLS Chemistry panel (creatinine, potassium, calcium, inorganic phosphorus, lactate dehydrogenase, and uric acid) will be performed real-time pre-dose, 4 - 6 hours post-dose and 24-hours post-dose for each venetoclax dose escalation, and as deemed necessary per investigator to monitor TLS.
- TLS Chemistry panel results (creatinine, potassium, calcium, inorganic phosphorus, lactate dehydrogenase, and uric acid) must be reviewed by the investigator in real time and prior to the subject's next dose to ensure appropriate subject management.

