## APPENDIX E. DEFINITIONS OF LABORATORY AND CLINICAL TUMOR LYSIS SYNDROME

Metabolic Abnormality	Criteria for Classification of Laboratory Tumor Lysis Syndrome	Criteria for Classification of Clinical Tumor Lysis Syndrome
Hyperuricemia	Uric acid > 8.0 mg/dL (475.8 $\mu$ mol/L) in adults	
Hyperphosphatemia	Phosphorus > 4.5 mg/dL (1.5 mmol/L) in adults	
Hyperkalemia	Potassium > 6.0 mmol/L	Cardiac dysrhythmia or sudden death probably or definitely caused by hyperkalemia
Hypocalcemia	Corrected calcium < 7.0 mg/dL (1.75 mmol/L) or ionized calcium < 1.12 mg/dL (0.3 mmol/L) a	Cardiac dysrhythmia, sudden death, seizure, neuromuscular irritability (tetany, paresthesias, muscle twitching, carpopedal spasm, Trousseau's sign, Chvostek's sign, laryngospasm, or bronchospasm), hypotension, or heart failure probably or definitely caused by hypocalcemia
Acute kidney injury b	Not applicable	Increase in the serum creatinine level of 0.3 mg/dL (26.5 $\mu$ mol/L) (or a single value > 1.5 $\times$ the upper limit of the age-appropriate normal range if no baseline creatinine measurement is available) or the presence of oliguria, defined as an average urine output < 0.5 mL/kg/hr for 6 hrs

a. The corrected calcium level in mg/dL = measured calcium level in mg/dL + 0.8  $\times$  (4-albumin in g/dL).

b. Acute kidney injury is defined as an increase in the creatinine level of at least 0.3 mg/dL (26.5  $\mu$ mol/L) or a period of oliguria lasting 6 hours or more. By definition, if acute kidney injury is present, the subject has clinical tumor lysis syndrome.

Note: In laboratory tumor lysis syndrome, 2 or more metabolic abnormalities must be present during the same 24-hour period within 3 days before the start of therapy or up to 7 afterward. Clinical tumor lysis syndrome requires the presence of laboratory tumor lysis syndrome plus an increased creatinine level, seizures, cardiac dysrhythmia, or death.

Source: Howard SC, Jones DP, Pui CH. The tumor lysis syndrome. N Engl J Med. 2011;364(19):1844-54.

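### SAP 10.3.2 calls its laboratory TLS rule the Howard criteria but applies the 1.75 mmol/L cut-off to unqualified calcium, where protocol Appendix E requires albumin-corrected or ionized calcium

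*SAP*

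**What the plan says.** SAP 10.3.2, on laboratory data, promises this output: "The number and percentage of subjects meeting the Howard criteria for TLS will be presented". It then sets the rule: "The Howard Criteria for TLS is defined as two or more of the following treatment-emergent lab changes within a 24-hour period". Four criteria follow: uric acid above 475.8 µmol/L, potassium above 6 mmol/L, inorganic phosphorus above 1.5 mmol/L and calcium below 1.75 mmol/L. The evaluation period runs from after the first dose to 7 days from it. The SAP mentions no correction, no albumin and no ionized calcium for this rule, here or elsewhere.

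Protocol Section 6.2 says "Definitions of laboratory TLS and clinical TLS are provided in" Appendix E, and names it there as the "Howard grading classification". The hypocalcemia row of Appendix E reads "Corrected calcium < 7.0 mg/dL (1.75 mmol/L) or ionized calcium < 1.12 mg/dL (0.3 mmol/L". Its footnote a begins "The corrected calcium level in mg/dL = measured calcium level in mg/dL + 0.8" and multiplies that factor by 4 minus albumin in g/dL. The closing note counts abnormalities from 3 days before therapy to 7 days after its start. It treats the clinical form separately: "Clinical tumor lysis syndrome requires the presence of laboratory tumor lysis syndrome plus an increased creatinine level, seizures, cardiac dysrhythmia, or death".

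On what is measured, Section 6.2 says: "TLS Chemistry panel (creatinine, potassium, calcium, inorganic phosphorus, lactate dehydrogenase, and uric acid) will be performed real-time pre-dose", with further samples after each dose escalation. Albumin is not in that panel. It is listed under clinical chemistry in Operations Manual 3.14, Table 1. Neither list includes ionized calcium.

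**The concern.** The SAP and the protocol use the same name and the same number for two different quantities. Measured and corrected calcium agree only at an albumin of 4 g/dL. A table described as applying the Howard criteria would therefore use a different hypocalcemia rule from the one the protocol calls Howard, and readers would not be told.

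TLS is an adverse event of special interest and is named in the secondary objective. The trial also asks whether outpatient initiation is safe, and Section 4.2 cites a clinical TLS rate below 1% across the AML program. Where few events are expected, a single misclassified subject is visible in the table.

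**Working it through.** **1. Is it the same cut-off?** Appendix E equates 7.0 mg/dL with 1.75 mmol/L, a factor of 1.75 / 7.0 = 0.25. The SAP uses 1.75 mmol/L, so the number comes across unchanged. The other three SAP cut-offs (475.8, 6 and 1.5) also match Appendix E. Only the calcium line has lost its qualifier.

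**2. Effect of the missing correction.** Inputs: the cut-off of 7.0 mg/dL and the footnote a formula, corrected = measured + 0.8 × (4 − albumin). Appendix E is met on its corrected-calcium limb when measured calcium is below 7.0 − 0.8 × (4 − albumin). The SAP is met when measured calcium is below 7.0. The documents give no albumin values, so those below are assumptions.

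| Albumin, g/dL (assumed) | Correction, mg/dL | Appendix E met if measured calcium is below | Measured calcium where the rules differ | SAP error |
|---|---|---|---|---|
| 2.5 | +1.2 | 5.8 mg/dL (1.45 mmol/L) | 5.8 to <7.0 mg/dL | over-counts |
| 3.0 | +0.8 | 6.2 mg/dL (1.55 mmol/L) | 6.2 to <7.0 mg/dL | over-counts |
| 3.5 | +0.4 | 6.6 mg/dL (1.65 mmol/L) | 6.6 to <7.0 mg/dL | over-counts |
| 4.0 | 0 | 7.0 mg/dL (1.75 mmol/L) | none | none |
| 4.5 | −0.4 | 7.4 mg/dL (1.85 mmol/L) | 7.0 to <7.4 mg/dL | under-counts |

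A subject with low ionized calcium but measured calcium at or above the cut-off is also missed by the SAP.

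**3. When does this change a classification?** Two abnormalities are needed. Four criteria give 6 pairs, of which 3 include calcium. If two other criteria are already met within the 24 hours, the subject is positive under either rule. Calcium decides only when it is one of exactly two abnormalities and lies in the discordant band, or is low on the ionized limb alone.

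**4. Size of one reclassification.** 1/60 = 1.7 percentage points overall. SAP 10.1 also reports by hypomethylating agent. If the split followed Study M14-358 (84:31, an assumption, since the agent here is the investigator's choice), 60 × 84/115 ≈ 44 and 60 × 31/115 ≈ 16. One subject would then be 1/44 = 2.3 or 1/16 = 6.3 points.

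**5. Is albumin available?** Operations Manual 2.1 schedules the clinical chemistry panel at Screening, pre-dose on Cycle 1 Day 1 and next on Day 28. The last scheduled 24-hour TLS sample falls on Day 4, or Day 5 for a four-day ramp-up. A Day 1 albumin would then be 3 or 4 days old, and at most 7 days old at the end of the window. Operations Manual 3.14 and 3.19 allow repeat and unscheduled tests, so a nearer value may exist.

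**6. The ionized limb.** 1.12 mg/dL × 0.25 = 0.28 mmol/L, which Appendix E prints as 0.3. The two units agree only after rounding, so the SAP must say which one it programs.

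**The case against.** The best defence is that this is one component of a descriptive safety count. No hypothesis test or interim analysis depends on it, the primary endpoint is untouched, and a programmer who knows Appendix E could take calcium to mean corrected calcium, using the Day 1 albumin. The low consequence stands. The implied correction does not: the SAP neither states it nor says which albumin to use, and the TLS panel contains none.

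Four stronger readings are tempting, and the documents do not support them:

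- **The trial's TLS rate as a whole is compromised.** SAP Table 1 counts reported adverse events by a narrow SMQ and does not use this rule. The two counts can differ whatever calcium rule is chosen.
- **Investigators are told to correct calcium generally, so site and SAP classifications will conflict.** In Appendix F that instruction sits only in the row for symptomatic hypocalcemia, and that row's own trigger is calcium without the word corrected.
- **Correction is impossible because the TLS panel lacks albumin.** Albumin is drawn pre-dose on Cycle 1 Day 1. The SAP is silent; the data exist.
- **The output hides that it is a laboratory definition.** It sits under laboratory data and is defined by laboratory changes. A clearer label helps, but this is not concealment.

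**Conclusion.** The mismatch is real. SAP 10.3.2 applies the Howard name and the Appendix E number to the wrong calcium measure, and no other SAP text supplies the correction. The error over-counts hypocalcemia when albumin is below 4 g/dL (on the corrected limb) and under-counts it when albumin is above 4 g/dL or only ionized calcium is low. A reader might infer that the reported laboratory TLS rate will be inflated. That would need the subjects' albumin values and the frequency of two-abnormality cases, and the documents give neither.

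The conclusion rests on a literal reading of the SAP; the band widths rest on assumed albumin values. Because calcium is decisive only in exactly-two cases, and the table is descriptive and separate from the adverse-event count, the severity is minor to should-fix.

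**What to change.** In SAP 10.3.2:

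1. Replace the calcium criterion with: corrected calcium < 1.75 mmol/L (7.0 mg/dL) by the Appendix E formula or, where an ionized result was recorded, ionized calcium < 1.12 mg/dL. Use the mg/dL figure because the printed 0.3 mmol/L is rounded.
2. Use the recorded albumin closest in time to the calcium sample, including unscheduled values. This will normally be Cycle 1 Day 1 pre-dose, otherwise Screening. If there is none, use measured calcium and footnote how many subjects this affects.
3. Label the output: Treatment-emergent laboratory TLS (Howard laboratory thresholds; first dose to 7 days after it only). Footnote that the 3-day pre-therapy window and the clinical form in Appendix E are not included. Without that footnote, a label citing Appendix E would still be inaccurate.

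The cost is SAP wording and a few lines of programming, with no new sampling. There are two limits. Albumin will usually be carried forward from baseline, and a Screening value may have been drawn up to 21 days before the first dose, or longer where the Medical Monitor has agreed. Ionized calcium is not a scheduled test, so that limb applies only where a site measured it and the result was recorded.
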